## 6.7. Prohibited Therapies and/or Medications

Safety assessment will not be influenced by exposure to prohibited medications.

The influence on efficacy caused by other prohibited medications will be reviewed in BDR meeting.

If a subject has been exposed to other antidiabetic medications during the trial, then all values of efficacy after the first exposure to other antidiabetic medications will be set to missing. In sensitivity analyses, the last value before the first exposure to other antidiabetic medications will be imputed using LOCF method.

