##### **The following medications are strictly prohibited unless for special medical condition**

- Any antidiabetic drug (including traditional Chinese medicine) other than the study medications (starting from the run-in period)

- Hypoglycemic healthcare product
- Oral or injectable or inhaled glucocorticoid
- Any known potent or moderate liver enzyme CYP450 3A4 inducers/inhibitors, including but not limited to:

Potent liver enzyme inducers: barbitals (especially phenobarbital), carbamazepine, diphenylhydantoin sodium, rifampin, dexamethasone, etc.

Potent liver enzyme inhibitors: ketoconazole, itraconazole, voriconazole, posaconazole, clarithromycin, indinavir, ritonavir, saquinavir, telithromycin, Boceprevir, nelfinavir, Telaprevir, conivaptan, nefazodone.

- Any unauthorized drugs (i.e., investigational drugs not marketed yet).

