## 4. Analysis Population

Table 1. Definition of Analysis Population

Population	Definition	Analyses Evaluated
Randomized Analysis Set (RAND)	

➤ All randomized subjects

➤ Any subject, who has been successfully randomized, will be included

	

➤ Study Population

➤ Demographics, Baseline Characteristics

Safety Analysis Set (SS)	

➤ All randomized subjects who received at least one study dose

➤ A subset of RAND

➤ Analyses will be performed based on actual treatments subjects received

	

➤ Safety

Full Analysis Set (FAS)	

➤ All randomized subjects who received at least one study dose and had at least one post-treatment measurement of the primary efficacy endpoint on basis of the intention-to-treat approach

➤ A subset of Safety Set

➤ Analyses will be performed based on actual treatments subjects randomized

	

➤ Efficacy

➤ Baseline Characteristics

Population	Definition	Analyses Evaluated
Per Protocol Set (PPS)	

➤ All subjects without any major protocol deviations, which will be reviewed and determined in Blind Data Review Meeting before DBL

➤ A subset of Full Analysis Set

➤ Analysis will be performed based on actual treatments subjects randomized

	

➤ Efficacy

➤ Baseline Characteristics

Analysis population of each table and listing will be annotated in attached Table Shell.

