## 5. General Conventions of Statistical Analysis.

Two efficacy and safety statistical analysis will be performed for double-blinding period and the whole treatment period (at most to 52nd week) independently.

For categorical variables, the number and percentage of subjects for each category are calculated. For continuous variables, the descriptive statistics such as sample size (n), mean, standard deviation (SD), median, 1st quartile, 3rd quartile, minimum, and maximum are provided.

Unless otherwise specified, the significant level for between-group comparison is set as 0.05 (two-sided).

Efficacy analysis will be conducted according to the intention-to-treat (ITT) approach. All randomized subjects will be included in the intended treatment group no matter what happens (eg drop-out or treated incorrectly).

Analysis will be summarized by visit (See chapter 6.6 for detailed mapping rules). Data observed in all visits, including scheduled visit, unscheduled and end of treatment visit will be listed and sorted by treatment group, study center, subject ID and visit (if available).

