## 8. Primary Statistical Analyses

### 8.1. Primary Efficacy Analyses

The primary endpoint for this study is the change of HbA1c from baseline at double-blind treatment period completion (Week 24). Mixed Model for Repeated Measures (MMRM) without consideration of missing value imputation will be applied on FAS.

This model includes the factors of treatment group, visit, the interaction of visit with treatment group, pooled site, and baseline HbA1c.

Treatment group, visit, interaction of visit with treatment group, pooled site and HbA1c baseline value will be specified as the fixed effects.

An unstructured variance-covariance structure will be used for the within-subject error.

The Kenward and Roger method will be applied to estimate the degrees of freedom of the denominator.

If the model failed to converge, Heterogeneous first-order autoregressive, ARH (1), covariance structures would be adopted.

The adjusted mean difference of change from baseline between groups at fixed time points will be estimated and tested accordingly.

The primary comparison is the difference in the change from baseline in HbA1c at the end of double-blind treatment period (Week 24) between treatment groups. The point estimate and 95% CI of mean difference between treatment groups (HMS5552 75mg BID vs. Placebo BID) will be calculated. The significance level of the between-group comparison is 0.05 (2-sided). If  $p < 0.05$ , it suggests that the between-group difference is statistically significant. If the upper limit of the 95% CI is less than 0, it may be claimed that HMS5552 is superior to the placebo in treatment effect.

Below is the sample SAS code of MMRM:

```
proc mixed data=dataset;
  class TREATMENT CENTRE VISIT PATIENT;
  model CHG = TREATMENT VISIT TREATMENT*VISIT CENTRE BASELINE /
  solution ddfm=kr;
```

---

```
repeated VISIT / subject=PATIENT type=un;  
lsmeans TREATMENT*VISIT/ diff cl alpha=0.05;  
run;
```

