### 8.1.1. Sensitivity Analyses of Primary Efficacy endpoint

1. The same analysis for the primary endpoint will be performed in PPS as in FAS.
2. Primary efficacy analysis based on LOCF imputation.

Change from baseline in HbA1c when treatment completed (Week 24) will be described for each group. ANCOVA will be used to compare the change from baseline (LOCF) between treatment groups. The model includes treatment group, pooled site, interaction of pooled site with treatment group and baseline HbA1c. If the interaction is not significant (2-sided alpha 0.1), then remove the interaction of pooled site with treatment group from model. A superiority test between treatment group and placebo group will be performed. Based on covariance analysis model, difference of adjusted mean between treatment group and placebo group, as well as its 95% CI, will be estimated.

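### SAP 6.7 deletes HbA1c values observed after any other antidiabetic drug, and every planned Week-24 HbA1c change analysis inherits the deletion, so none tests it

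*Supplement*

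**What the plan says.** **The deletion rule.** SAP 6.7 states that after other antidiabetic use "all values of efficacy after the first exposure to other antidiabetic medications will be set to missing". For the sensitivity analyses it adds: "In sensitivity analyses, the last value before the first exposure to other antidiabetic medications will be imputed using LOCF method". Protocol v1.1 section 4.4.2 shows how broad the class is: "Any antidiabetic drug (including traditional Chinese medicine) other than the study medications (starting from the run-in period".

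**The label.** SAP 5 states: "Efficacy analysis will be conducted according to the intention-to-treat (ITT) approach". It goes on: "All randomized subjects will be included in the intended treatment group no matter what happens (eg drop-out or treated incorrectly".

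**The analyses of Week-24 HbA1c change.**
- Primary, SAP 8.1: "Mixed Model for Repeated Measures (MMRM) without consideration of missing value imputation will be applied on FAS".
- First sensitivity analysis, SAP 8.1.1: "The same analysis for the primary endpoint will be performed in PPS as in FAS".
- Second sensitivity analysis, SAP 8.1.1: ANCOVA on LOCF-imputed data.

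SAP 4 defines the FAS as "All randomized subjects who received at least one study dose and had at least one post-treatment measurement of the primary efficacy endpoint". SAP 4.1 removes from the PPS anyone without valid Week-24 HbA1c.

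**The protocol.** Section 9 has no rule that discards values after other antidiabetic use. For early withdrawals, the LOCF in 9.3.6 carries forward the last available post-treatment measurement. Section 9.3 asks the SAP to record departures from the planned analysis. The table in SAP 2.1 lists two changes (the wording of the alternative hypothesis and the added exploratory endpoints) and not this one.

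**The concern.** A sensitivity analysis is useful when it relaxes a choice that the primary analysis makes. Here the choice is to discard measured HbA1c values once another antidiabetic has been taken, and both sensitivity analyses make it too. They vary the population and the treatment of the resulting gap, but never put the discarded values back.

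Other antidiabetic use plausibly follows poor control, so it may be commoner on placebo. If so, the discarded placebo values would tend to be the ones lowered by the extra drug, and leaving them out would make the difference larger than the one observed. An effect as if no other drug had been taken is a legitimate target. It is not what most readers understand by intention-to-treat, and the plan offers nothing to show whether the conclusion depends on the distinction.

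**Working it through.** **1. How the rule reaches each analysis**

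| Week-24 HbA1c change analysis | What happens to values after exposure |
|---|---|
| MMRM, FAS (8.1) | Absent; handled under missing at random |
| MMRM, PPS (8.1.1) | Week 24 is missing, so 4.1 takes the subject out |
| ANCOVA with LOCF (8.1.1) | Replaced by the last value before exposure (6.7) |

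None of the three uses the observed values. The response rates below 7% and 6.5% (9.1.2, 9.1.3) also rest on LOCF data.

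**2. What one exposure removes.** Double-blind HbA1c is scheduled at Weeks 4, 8, 12, 16, 20 and 24. A single day of another drug in Week 5 deletes Weeks 8 to 24, which is 5 of 6 values. Exposure before the Week 4 visit deletes all 6, and the subject then contributes no response to the MMRM. The SAP does not say whether a value set to missing still counts toward FAS membership.

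**3. The plan's own power figure.** Inputs from SAP 2.4: 450 subjects at 2:1 (300 and 150), SD 1.2, difference 0.4, two-sided alpha 0.05.
- Standard error = 1.2 × √(1/300 + 1/150) = 1.2 × 0.1 = 0.12.
- Power ≈ Φ(0.4/0.12 − 1.96) = Φ(1.373) = 91.5%. The noncentral t with 448 df gives 91.4%, the stated figure.

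**4. Possible size of the shift.** The documents give neither the frequency of other antidiabetic use nor its effect, so the following are assumptions: exposure p(placebo) = 5-15%, p(HMS5552) = 2-5%, and a further HbA1c reduction g = 0.5-1.0 points, equal in both arms and sustained to Week 24, with every exposed subject measured at Week 24. Take 0.4 as the difference without other drugs. Then:

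shift = [p(placebo) − p(HMS5552)] × g; all-observed difference = 0.4 − shift; power ≈ Φ(difference/0.12 − 1.96).

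| Placebo / HMS5552 | g | Shift | Difference | Power |
|---|---|---|---|---|
| 5% / 5% | 0.5 or 1.0 | 0 | 0.400 | 91.5% |
| 5% / 2% | 0.5 | 0.015 | 0.385 | 89.4% |
| 10% / 3% | 1.0 | 0.07 | 0.330 | 78.5% |
| 15% / 5% | 1.0 | 0.10 | 0.300 | 70.5% |
| 15% / 2% | 1.0 | 0.13 | 0.270 | 61.4% |

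The range is 0 to 0.13 points; 0.13/0.4 = 32.5%, or about 33%. At 2% / 1% with g = 0.5, which is rarer use than assumed above, the shift is 0.005. Steps 2 and 4 describe different subjects: one day of drug in Week 5 deletes five values, but g at Week 24 would then be close to zero.

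**The case against.** **The intention-to-treat wording.** A reader might infer that 6.7 flatly contradicts SAP 5 by dropping randomized subjects. The text does not support that. SAP 5 mainly promises that subjects are kept in their assigned group. SAP 6.7 deletes values, and an exposed subject with an earlier post-baseline HbA1c stays in the model under the randomized arm. What stands is narrower: the label does not tell the reader that follow-up is cut off at other antidiabetic use.

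**Other causes.** A reader might also infer that 6.7 alone prevents a full intention-to-treat comparison. It does not. The FAS requires a dose and a post-treatment HbA1c, no efficacy visits are described after the termination visit, and SAP 6.6 maps end-of-treatment values only within 7 days.

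**Few values may exist.** This is the strongest objection. Other antidiabetics are prohibited, and protocol 4.5.2 places the termination visit before routine treatment starts for subjects withdrawn for hyperglycemia. That route should yield few post-exposure values. It does not close the matter. The prohibition allows for special medical conditions and covers traditional Chinese medicine, and the withdrawal reasons in 4.5 do not name prohibited-drug use. On withdrawal itself, 4.4.2 says a subject meeting the hyperglycemia criterion will be discontinued, whereas 4.5.2 leaves this to the investigator's evaluation; those two passages should be reconciled. Subjects can therefore remain in the trial and be measured, which is the case that 6.7 provides for.

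**Missing at random.** If use follows poor control already visible in earlier HbA1c, the MMRM's assumption may be reasonable. That is a fair point: the assumption is untested here, not shown to fail.

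**Conclusion.** The concern holds in limited form. All three planned Week-24 HbA1c change analyses share one deletion rule, so the plan cannot show whether the result holds with the values observed. The rule is absent from protocol section 9 and undeclared in SAP 2.1, and the analysis it produces is described only as intention-to-treat.

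No bias of known size follows. The 0 to 0.13 points (0-33% of 0.4) rest wholly on assumed exposure rates and a sustained effect, and the shift is near zero if use is rare, brief or balanced between arms. Nor is the primary analysis wrong in itself: its target can be defended if it is named. This is an inexpensive improvement worth making, not a fault that undermines the trial.

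**What to change.** 1. Add to SAP 8.1.1 a sensitivity analysis: the same MMRM on the FAS, using every observed double-blind HbA1c value regardless of other antidiabetic use.
2. State in SAP 5 and 8.1 that the primary analysis excludes values after other antidiabetic use and so estimates the effect as if none had been taken, under missing at random.
3. List the rule in SAP 2.1 as a change from protocol section 9, with the reason.

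The cost is SAP wording and one extra model run on data already in the database; no visit, data collection or clinical rule changes. The added estimate may be slightly less favourable. It will not recover values never collected after withdrawal, and it should not be presented as a full treatment-policy analysis.

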## 7. Study Population Analyses

### 7.1. Disposition of Subjects

Unless otherwise specified, disposition of randomized subjects will be summarized for each treatment group. Summarization will be performed for the double-blind treatment period and the whole treatment period (52 weeks at most) respectively.

The number of screened subjects, the number of run-in period subjects, the number and percentage of each analysis set (RAND, SS, FAS and PPS) will be summarized. Subjects in each analysis set will be listed. The number and percentage of subjects who participate in open-label treatment period (for whole study only) will be summarized.

The number and percentage of subjects who complete the study and the withdrawal reasons will be summarized.

The number and percentage of subjects who are excluded from SS, FAS and PPS will be summarized respectively.

### 7.2. Demographic and Baseline Characteristics

Demographics will be summarized for RAND. Baseline characteristics will be summarized for RAND, FAS and PPS.

Demographic characteristics, medical history and concomitant diseases will be summarized based on RAND by treatment group and overall. Baseline of disease characteristics, vital signs, 12-lead ECG, hematology, chemistry and routine urine test will be summarized based on RAND, FAS and PPS by treatment group and overall. Listing of demographic data will be provided by subjects. Major and minor protocol deviations will be summarized based on RAND. Listings of major and minor protocol deviations will be provided.

For continuous variables, number, mean, standard deviation, median, minimum, maximum, 1st quantile and 3rd quantile will be calculated.

- Demographics includes age, height, weight, BMI, blood pressure, respiration, heart rate and body temperature.
- Baseline characteristics includes Baseline HbA1c, baseline fasting plasma glucose, baseline 2-hour postprandial plasma glucose and duration of type 2 diabetes.

---

For categorical variables, the number and percentage of each category will be displayed.

- Demographics category includes age ( $\leq 65$ ,  $> 65$ ), nationality, race, sex, BMI ( $< 24$ ,  $24-28$ ,  $\geq 28$ )
- Baseline disease characteristics category includes HbA1c ( $\leq 8.5\%$ ,  $> 8.5\%$ ).

### **7.3. Exposure to Study Drug and Compliance**

For study drug exposure and compliance, mean, standard deviation, minimum, maximum, median, 1st quantile and 3rd quantile of exposure (dose and days) and compliance will be calculated by subjects in each treatment group. The number and percentage of subject with poor compliance in each group (compliance  $< 80\%$  or compliance  $> 120\%$ ) will be provided.

### **7.4. Prior and Concomitant Medication**

Concomitant treatment will be coded using the World Health Organization (WHO) Drug dictionary and be summarized by ATC level 4 and preferred term. If ATC level 4 is missing, then it will be imputed with level 3. If ATC level 3 is missing, then it will be imputed with level 2. Concomitant medications will be summarized for prior to run-in period, during run-in period and during treatment period. Concomitant medications will be summarized following rules below.

Definition 1: According to the start date of concomitant medication prior to run-in period, during run-in period and during treatment period, it will be classified as concomitant medication prior to run-in period, concomitant medication during run-in period and concomitant medication during treatment period.

Definition 2: Concomitant medications will be determined by start/end time of concomitant medications. Once exposed to concomitant medications during prior run-in period, run-in period and treatment period then those concomitant medications will be summarized in corresponding periods. For example, if the start date of one concomitant medication is in run-in period and the end date is also in run-in period, then the concomitant medication will only be summarized in run-in period. If the start date of one concomitant medication is in run-in period and the end date is in treatment period, then the concomitant medication will be summarized in run-in period and treatment period.

When start date and end date of concomitant medications are missing, please refer to [Section 6.1.2](#) for imputation rules.

Usage of all concomitant medications will be listed based on randomized analysis set.

## 8. Primary Statistical Analyses

### 8.1. Primary Efficacy Analyses

The primary endpoint for this study is the change of HbA1c from baseline at double-blind treatment period completion (Week 24). Mixed Model for Repeated Measures (MMRM) without consideration of missing value imputation will be applied on FAS.

This model includes the factors of treatment group, visit, the interaction of visit with treatment group, pooled site, and baseline HbA1c.

Treatment group, visit, interaction of visit with treatment group, pooled site and HbA1c baseline value will be specified as the fixed effects.

An unstructured variance-covariance structure will be used for the within-subject error.

The Kenward and Roger method will be applied to estimate the degrees of freedom of the denominator.

If the model failed to converge, Heterogeneous first-order autoregressive, ARH (1), covariance structures would be adopted.

The adjusted mean difference of change from baseline between groups at fixed time points will be estimated and tested accordingly.

The primary comparison is the difference in the change from baseline in HbA1c at the end of double-blind treatment period (Week 24) between treatment groups. The point estimate and 95% CI of mean difference between treatment groups (HMS5552 75mg BID vs. Placebo BID) will be calculated. The significance level of the between-group comparison is 0.05 (2-sided). If  $p < 0.05$ , it suggests that the between-group difference is statistically significant. If the upper limit of the 95% CI is less than 0, it may be claimed that HMS5552 is superior to the placebo in treatment effect.

Below is the sample SAS code of MMRM:

```
proc mixed data=dataset;
  class TREATMENT CENTRE VISIT PATIENT;
  model CHG = TREATMENT VISIT TREATMENT*VISIT CENTRE BASELINE /
  solution ddfm=kr;
```

---

```
repeated VISIT / subject=PATIENT type=un;  
lsmeans TREATMENT*VISIT/ diff cl alpha=0.05;  
run;
```

### 8.1.1. Sensitivity Analyses of Primary Efficacy endpoint

1. The same analysis for the primary endpoint will be performed in PPS as in FAS.
2. Primary efficacy analysis based on LOCF imputation.

Change from baseline in HbA1c when treatment completed (Week 24) will be described for each group. ANCOVA will be used to compare the change from baseline (LOCF) between treatment groups. The model includes treatment group, pooled site, interaction of pooled site with treatment group and baseline HbA1c. If the interaction is not significant (2-sided alpha 0.1), then remove the interaction of pooled site with treatment group from model. A superiority test between treatment group and placebo group will be performed. Based on covariance analysis model, difference of adjusted mean between treatment group and placebo group, as well as its 95% CI, will be estimated.

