## 2.4. Sample Size Determination

This study plans to recruit 450 subjects. The number of subjects may be increased by 20% if drop-out is considered. The total number of subjects will be no more than 564. Subjects are randomized at a ratio of 2:1 to the experimental group (HMS5552) or the control group (placebo), it is estimated that no more than 376 subjects in the experimental group and 188 subjects in the control group will be included.

Based on the planned sample size and the treatment assignment ratio (450 subjects, HMS5552 experimental group: control group = 2:1), a power of 91.4% would be provided to detect a difference of at least 0.4% in the change of HbA1c from baseline at week 24 between experimental group and control group, assuming there is no difference between the two groups with the standard deviation of 1.2% and the significance level of 0.05 (2-sided).

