## 4.1. Protocol Deviation

A listing of all protocol deviations will be provided. Protocol deviations will be reviewed at Blind Data Review (BDR) meeting and categorized into Major or Minor. The analysis population will be determined in BDR meeting.

Subjects will be excluded from Per Protocol Set (PPS), when

1. Compliance in double-blind treatment period is less than 80% or greater than 120%.
2. No valid HbA1c data in Week 24.

Major protocol deviations, which leads to exclusion from PPS, will be reviewed and finalized at Blind Data Review meeting.

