## 6. General Conventions For Data Handling

### 6.1. Premature Withdraw and Missing Data

In FAS, missing data will be imputed by LOCF method for ANCOVA. Missing values will be imputed with the last non-missing available on-treatment assessment (including unscheduled visit). If categorical parameter is derived with quantitative parameters, the derivation will be conducted after missing data imputation of quantitative parameter is completed.

When month and day of birth date are missing, then “July” and “15th” will be used to impute the missing month and missing day respectively. Same imputation rule will be used to impute the missing initial diagnosis date of type II diabetes.

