### **9.1.2 Hba1c Response Rate (proportion of subjects with HbA1c< 7%)**

HbA1c Response Rate and composite HbA1c response rate will be calculated on basis of data imputed using LOCF method. The percentage pf subjects that with HbA1c < 7% at the end of double-blind treatment period (Week 24) will be summarized on basis of data imputed using LOCF method. Odds ratio (OR) and its 95% CI between two treatment groups will be estimated using logistic regression method. The model includes the factors of treatment group, pooled site, interaction of pooled site with treatment group and baseline HbA1c. If the interaction is not significant (2-sided alpha 0.1), then remove the interaction of pooled site with treatment group from model.

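### The two sensitivity analyses do not test whether the Week 24 result survives if HMS5552 dropouts lose their benefit after stopping, and the responder rates share the same LOCF

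*Supplement*

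**What the plan says.** SAP 8.1 analyses the Week 24 change in HbA1c by MMRM on the full analysis set, without imputation. SAP 8.1.1 then lists two sensitivity analyses.

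- **Per-protocol MMRM.** "The same analysis for the primary endpoint will be performed in PPS as in FAS". Under SAP 4.1 a subject leaves the per-protocol set if double-blind compliance is below 80% or above 120%, or if there is "No valid HbA1c data in Week 24".
- **LOCF ANCOVA.** SAP 6.1: "Missing values will be imputed with the last non-missing available on-treatment assessment (including unscheduled visit"). Protocol 9.3.6 names this as its only sensitivity analysis.

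On other antidiabetic drugs, SAP 6.7 says "all values of efficacy after the first exposure to other antidiabetic medications will be set to missing"; the sensitivity analyses carry the preceding value forward.

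For the responder endpoints, SAP 9.1.2 states "HbA1c Response Rate and composite HbA1c response rate will be calculated on basis of data imputed using LOCF method". SAP 9.1.3 (<6.5%) and 9.2.7 (composite) follow the same rule, and protocol 9.3.3 prescribes LOCF for the response rate.

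Follow-up after withdrawal is a termination visit and a safety telephone call (protocol 4.6). No HbA1c is taken at Week 24 from a subject who has left. Neither the SAP nor protocol v1.1 contains a delta, tipping-point, reference-based or non-responder analysis.

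**The concern.** A likelihood MMRM without imputation is valid if data are missing at random (MAR): given the observed values, subjects who leave would have continued like similar subjects who stay. Here missingness can be linked to outcome. Protocol 4.4.2 discontinues subjects who meet the hyperglycemia criterion (4.5.2 leaves this to the investigator's evaluation), and SAP 6.7 deletes values after other antidiabetic drugs. With no Week 24 HbA1c after withdrawal, the trial's data cannot test the assumption, so that task falls to the sensitivity analyses.

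The useful question is whether the conclusion holds if HMS5552 subjects who stop lose the drug's effect. The per-protocol repeat has no subject with a missing Week 24 value, so it cannot answer. LOCF fixes the benefit at its last on-treatment level, so it cannot show that loss either. If all three analyses agree, the report may claim robustness that was not examined.

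The responder rates have the same weakness. A subject who stops at Week 8 with HbA1c 6.9% is counted as a success at Week 24.

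**Working it through.** **The plan's own figure.** SAP 2.4 gives "450 subjects, HMS5552 experimental group: control group = 2:1" (300 and 150), "a power of 91.4% would be provided to detect a difference of at least 0.4" percentage points, and a "standard deviation of 1.2% and the significance level of 0.05 (2-sided").

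- SE = 1.2 × √(1/300 + 1/150) = 0.12.
- 0.40/0.12 = 3.33, and Φ(3.33 − 1.96) = 91.5%. The noncentral t with 448 degrees of freedom gives 91.41%.

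The stated 91.4% reproduces and is not in question. The plan's only figure on dropout is the 20% enrolment allowance.

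**Assumptions for the illustration (not from the documents unless noted).**

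- On-treatment effect at Week 24: 0.40, the planning difference.
- Share of that effect present at Weeks 4, 8, 12, 16 and 20: 35%, 65%, 85%, 95% and 100%.
- Dropout proportion d equal in both arms, with the last visit spread evenly over those five weeks; flat placebo course.
- Correlation 0.75 between any two visits (used only for copy-reference).

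**Expected Week 24 effect.**

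- MAR: 0.40.
- LOCF: the mean share carried is (0.35 + 0.65 + 0.85 + 0.95 + 1.00)/5 = 0.76, so dropouts keep 0.76 × 0.40 = 0.304. Overall: (1 − d) × 0.40 + d × 0.304.
- Jump-to-reference (dropouts lose all of it): (1 − d) × 0.40.
- Copy-reference: after k visits the carry-over is 0.75/(1 + 0.75(k − 1)) times the sum of the first k effects (0.14, 0.26, 0.34, 0.38, 0.40). This gives 0.105, 0.171, 0.222, 0.258 and 0.285, mean 0.208. Overall: (1 − d) × 0.40 + d × 0.208.

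| Dropout | MAR | LOCF | Copy-reference | Jump-to-reference |
|---|---|---|---|---|
| 10% | 0.40 | 0.390 | 0.381 | 0.360 |
| 20% | 0.40 | 0.381 | 0.362 | 0.320 |
| 25% | 0.40 | 0.376 | 0.352 | 0.300 |

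LOCF exceeds jump-to-reference by 0.030, 0.061 and 0.076 (8%, 19%, 25%), and copy-reference by 0.010, 0.019 and 0.024 (3%, 5%, 7%).

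**Simulation** (376 and 188 subjects, SD 1.2, same onset and correlation, 400 replicates, dropout at random; differences are HMS5552 minus placebo):

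| Dropout, drug/placebo | Completers | LOCF | Effect lost after stopping |
|---|---|---|---|
| 10%/10% | −0.405 | −0.397 | −0.365 |
| 20%/20% | −0.405 | −0.386 | −0.324 |
| 20%/10% | −0.397 | −0.382 | −0.320 |
| 10%/20% | −0.397 | −0.391 | −0.357 |

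Completers and LOCF both stay near 0.40 while the effect allowing for lost benefit falls. Because dropout here is random, the simulation does not show what outcome-related dropout would do to LOCF.

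**What a tipping point would report.** Take an observed difference of −0.40 with SE 0.12 held fixed. The upper 95% limit reaches zero when missing HMS5552 values are worse by (0.40 − 1.96 × 0.12)/d = 0.165/d. That is about 3.3 points at 5% missing, 1.65 at 10% and 0.82 at 20%.

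**Responders.** If dropouts meet the threshold under LOCF at the same rate as the rest, an assumed 40% rate becomes 0.40 × 0.90 = 36% at 10% dropout, or 0.40 × 0.80 = 32% at 20%, once dropouts count as non-responders.

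**The case against.** LOCF is not an MAR method. In the working above it gives dropouts 0.304 rather than 0.40, so it does let them do worse than MAR. A reader might infer that neither check departs from MAR at all; the arithmetic contradicts that. What stands against LOCF is that it offers one fixed departure and cannot represent loss of effect after stopping.

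A reader might also infer that LOCF must flatter HMS5552. The documents do not show this. Under protocol 4.5.2 a subject leaving for hyperglycemia must first complete the termination visit, where HbA1c is measured, so poor values are observed and can be carried forward. If such subjects are mostly on placebo, LOCF may widen the difference; if mostly on HMS5552, it may shrink it. SAP 6.6 also admits end-of-treatment values taken up to 7 days off drug, and protocol 4.5 allows re-entry within 2 weeks.

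SAP 9.2.8 compares time to hyperglycemia withdrawal by Kaplan-Meier and log-rank test. That makes outcome-related dropout visible, but it does not show what the dropout does to the HbA1c estimate.

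A per-protocol set that requires the Week 24 value is a recognisable choice. Deleting the requirement would only return that analysis to MAR, so it is no remedy here.

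For the composite, one might infer that early leavers are credited with freedom from hypoglycemia over a shortened exposure. SAP 9.2.7 does not say how that component is handled after withdrawal, and SAP 2.1 labels the endpoint exploratory.

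**Conclusion.** The gap is real and cheap to close. Neither planned check tests loss of benefit after stopping: one excludes the subjects concerned, and the other applies a single assumption that keeps their last on-treatment level. The responder rates share that assumption.

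The size depends on actual dropout, which the documents do not report; 20% is a planning allowance. Under full loss of effect with equal, evenly spread dropout, LOCF stands 0.03 to 0.08 HbA1c points above jump-to-reference for dropout of 10% to 25%. The 19% relative gap at 20% dropout belongs to that scenario alone; under copy-reference it is about 5%. Jump-to-reference is not the truth either: without Week 24 data after withdrawal, it is a chosen stress scenario. The point does not show that the primary conclusion is wrong, only that its robustness would not be tested.

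**What to change.** - Keep the MMRM as the primary analysis.
- In SAP 8.1.1 add, on the FAS, a control-based multiple imputation (for example jump-to-reference) and a delta tipping-point analysis that worsens missing HMS5552 values until significance is lost.
- Keep the LOCF ANCOVA, which protocol 9.3.6 names, and the per-protocol MMRM as supportive. Do not present either as a test of the missing-data assumption.
- For the <7.0%, <6.5% and composite endpoints, add an analysis that counts a Week 24 HbA1c as non-response if it is missing or taken after another antidiabetic drug. If this replaces LOCF as the main responder analysis, record the departure from protocol 9.3.3 in SAP 2.1.

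The cost is SAP text, some extra programming and slightly less favourable responder rates. No new data or visits are needed.
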